1.0 Introduction

Continuous vital sign monitoring is a basic tenet of specialized care in the developed world that is vastly underutilized during hospital or clinic admissions or outpatient routine visits in most low-and-middle income countries (LMICs). Despite the positive outcomes associated with vital sign monitoring (i.e., increased survival-to-discharge rates, lower complication rates and shorter length of stay in hospital),¹ the prohibitive costs of conventional patient monitors and the difficulty in maintaining complex medical equipment limit its practice in the developing world.

Wearable health devices (WHDs) are increasingly helping people better monitor their health status both at an activity/fitness level for self-health tracking and at a medical level providing more data to healthcare providers to increase the potential for early diagnosis and guidance of treatment. Key advancements in technology are enabling the creation of smaller computers than ever before; allowing wearable technology to incorporate miniaturized systems to enhance the quality and convenience of patient care.¹ Advances in materials science, chemical analysis techniques, equipment design and manufacturing methods have further laid the foundation for the continuous evolution of wearable systems over the years.²

WHDs when properly designed, implemented and adopted can provide ample benefits for healthcare providers and patients. Wearable technologies like Apple watch, Fitbit, Jawbone, ViSi Mobile and Vital Connect wireless patch have been used in tracking personal physiological and biological parameters for routine activity performance and/or clinical monitoring.^{3,4} These devices collect data such as heart rate, stress levels, obesity, oxygen saturation, blood pressure and calories; and serve a broad range of use cases from newborn to elderly patients in different settings such as hospitals, nursing homes and homecare settings.

Measurement of vital signs in both in- and out-patient departments and during community outreach activities is necessary to assess the clinical situation of the patient and capture early warning scores for deterioration. The currently practice in most LMICs is for a clinician to take routine vital sign measurements intermittently and manually record these on a clinical chart. However, this leaves a lot of room for missed detection of early warning scores. Delays in diagnosing clinical deterioration prevent clinicians from taking corrective actions and are associated with increased complication rates and mortality. The use of wearable devices for long term monitoring is intended to provide instant diagnosis of acute events that will in turn lead to more effective and timely treatment of patients.⁵ Furthermore, the situation becomes more dire during community outreach activities (i.e., child health week, community ANC outreach, etc.), which are usually conducted by limited clinicians and several community health workers (CHWs).

In contrast to the traditional monitoring devices that have been in use in clinical settings, WHDs may be more suited to the constraints of low-resources settings. Conventional medical equipment frequently fail in health facilities in LMICs due to complex design and specifications, and environmental constraints including power instability, internet access, space limitations and availability of spare parts. This calls upon the need for more feasible innovations to improve on the quality of care for people living in LMICs. WHDs offer a promising solution.

Currently, due to lack of medical supplies, most ANC clinics – within the health facilities or during outreach activities – do not monitor for vital signs and blood pressure among pregnant women. While many devices exist, their ease of use and high-cost, including maintenance costs, hinder screening and monitoring programs in low resource settings. Accurate and low-cost vital sign monitoring devices are required to improve identification and treatment of women with danger signs during their routine ANC visits. To meet the growing demand for vital sign monitors during the COVID-19 pandemic, Neopenda has adapted an affordable, wearable, wireless vital sign monitoring solution (neoSpotTM), that measures temperature, respiration rate, blood oxygen saturation, pulse rate, and blood pressure.

1.1 Previous research on the neoSpotTM product

The neoSpotTM system is a new prototype in the series of vital sign monitors designed by Neopenda. The product is an iteration of the current vital signs monitor, neoGuardTM, which provides continuous measurement of pulse rate (PR), peripheral blood oxygen saturation (SpO₂), respiratory rate (RR) and temperature to patients in tertiary care settings. The neoSpotTM system has been developed to capture instantaneous readings in settings such as community outreaches or lower-level health facilities, where reliable vital sign measurement equipment is not readily accessible. Since the new product will comprise of similar hardware and algorithms to its precursor, neoGuardTM, it is expected to perform at the same level of accuracy for measurement of PR, SpO₂, RR and temperature. Measurement of an additional parameter, blood pressure (BP), is in the early stage of development and will add substantial value to the previous product. The data generated from this study will help in the final integration of BP measurement to the neoSpotTM system. While this will be the first field study on neoSpotTM itself, related research has been conducted on the precursor system, neoGuardTM, as detailed below. Our path to evaluating and developing neoSpotTM into a commercial product will follow a similar pathway.

Table 1. *Research history of Neopenda's wearable vital signs monitors*

Timeline	Location	Device Version	Description	Purpose	Sample Size	Status
Jul 2019	TMC, Boston, MA, USA	neoGuard V1.0	Pilot study	Evaluate and refine signal quality	22 neonates	Complete
Oct 2019	Jinja RRH	neoGuard V2.0	Pilot study	Evaluate preliminary accuracy	27 infants and stable neonates	Complete
Sep 2020	Clinimark Laboratories	neoGuard V3.0	Accuracy study	Validation of final accuracy	15 healthy adults	Complete
Oct 2020	UCSF Hypoxia Lab	neoGuard V3.0	Accuracy study	Validation of final accuracy	15 healthy adults	Complete
Feb 2021	Jinja RRH	neoGuard V3.0	Feasibility study	Evaluate preliminary accuracy	30 adult patients	Complete
Mar-May 2021	Kenya	neoGuard V3.0	Feasibility study	Evaluate feasibility and efficacy	172 neonates	Complete

Mar-May 2022	Nigeria	neoGuard V3.0	Feasibility study	Evaluate feasibility and efficacy	~225 neonates	Ongoing
Apr 2022 – Apr 2023	Kenya	neoGuard V3.0	Interrupted time series study	Evaluate clinical impact and cost-effectiveness	~3,000 neonates	Ongoing
Jun-Sep 2022	Zambia	neoSpot V1.0	Feasibility study		~100 pregnant women	Submitted for IRB approval

V3.0* - these are commercial equivalent units

2.0 Statement of the problem

Few innovations are currently available to help overburdened clinicians and community health volunteers better manage the high quantity of patients. In the neoSpot solution, researchers are taking a known and proven science of clinical vital signs monitoring, and re-imagining it for the users and the constraints of low-resource environments. The current practice at most ANC clinics in LMIC settings is intermittent, manual measurement of vital signs or blood pressure. Nurses and Community Health Volunteers must manually count heart beats or breaths—at best every few hours—or share the few available, functioning devices, such as pulse oximeters, which only intermittently measure oxygen saturation and pulse. This practice is insufficient for early detection of danger signs and optimal management of critical care patients.

Furthermore, gold standard monitors used in the U.S. and other high-resource areas, such as from Covidien, Masimo or Philips, are prohibitively expensive, inappropriately designed, and challenging to maintain or repair. They fail to meet unique sets of environmental constraints such as unstable power supply, lack of internet access, and heat & humidity. If donated to a low-resource environment, they quickly fail or end up obsolete within short periods of use. Existing products in the global health space do not meet the need for continuous monitoring in the clinical setting (e.g. Lifebox pulse oximeter), only measure 1 or 2 parameters (e.g. BempuTemp Watch and NeMoCare) and/or are geared toward diagnosing specific conditions (e.g. pneumonia diagnostics like the Philips CHARM).

Neopenda's solution intends to improve the quality of patient care over the standard-of-care and addresses the unmet need for a feasible way to monitor multiple key vital signs. The neoGuard™ product is designed to operate in dynamic clinical environments with space constraints, unreliable power supply and limited numbers of health staff. At less than a 1/10th of the average cost of conventional patient monitors (\$230 vs. \$2,500), the neoSpot™ technology provides an affordable and sustainable vital sign monitoring solution. The wearable band is bio-compatible, reusable and easy to sterilize, ensuring that there are no additional costs spent on single-use accessories.

NeoSpot™ has been developed and tested with feedback from more than 100 health workers with varying levels of clinical expertise and technical prowess to ensure that it is intuitive to a wide range of users including lower skilled personnel like nursing assistants and community health workers in remote settings. This human-centered design approach has been used to preempt the challenge of usability that can occur when transitioning new technologies to diverse users in different cultural contexts.

3.0 Rationale/Justification

Many novel interventions are introduced to LMICs with little-to-no evidence of their successful performance, applicability, effectiveness, and feasibility and acceptability by the providers. There is need for robust testing and evaluation of innovations to ensure that they serve their intended purposes before they are introduced into common practice. The justification for this study is the need to generate evidence of feasibility and acceptability for neoSpot™ on pregnant women, so as to inform any changes or considerations for its use in LMIC settings. This proposed study is unique, impactful, and scalable given the immediate clinical application by CHWs during community ANC visits.

If the NeoSpot device shows to be feasible and acceptable for use by CHWs and by pregnant women, there would be sufficient evidence to support the use of the device to measure vital signs and blood pressure among pregnant women. This study has the potential to improve access vital signs measurements during both community and clinic activities as it would increase identification and improve treatment of pregnant women with danger signs such as eclampsia/pre-eclampsia, fever, etc. in low-resource settings and would serve the larger aim of reducing maternal and neonatal morbidity and mortality.

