4.0 Theoretical/conceptual framework

This study is a feasibility trial, which is designed to demonstrate the feasibility and acceptability of this novel platform when used by community health workers (CHWs) on pregnant women to check their vital signs during community ANC outreach activities.

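### Section 3.0 treats a feasible and acceptable result as sufficient evidence for using NeoSpot to measure blood pressure, a conclusion that the protocol's own account of blood pressure does not support

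*Combined protocol and SAP*

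**What the plan says.** Section 3.0 (Rationale/Justification) sets one condition, that NeoSpot is feasible and acceptable to community health workers (CHWs) and pregnant women. It concludes that "there would be sufficient evidence to support the use of the device to measure vital signs and blood pressure among pregnant women". The sentence contains no condition on accuracy. The same section calls for testing of innovations to "ensure that they serve their intended purposes before they are introduced into common practice", and describes the study as impactful and scalable "given the immediate clinical application by CHWs during community ANC visits".

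Section 1.1 says of BP: "Measurement of an additional parameter, blood pressure (BP), is in the early stage of development". It adds: "The data generated from this study will help in the final integration of BP measurement to the neoSpotTM system". For pulse rate, oxygen saturation, respiratory rate and temperature, it argues from the similar hardware and algorithms of the precursor, neoGuard, that "it is expected to perform at the same level of accuracy". It also acknowledges the limit of that history: "While this will be the first field study on neoSpotTM itself".

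Section 4.0 describes the trial as "designed to demonstrate the feasibility and acceptability of this novel platform". Accuracy is not mentioned there.

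**The concern.** Feasibility and acceptability show that a device can be used and that people are content to use it. They do not show that its readings are right. The Rationale moves from the first to the second without an accuracy step, and for BP the protocol elsewhere says that this step has not been reached.

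At stake is what the trial may be said to have shown. Taken at its word, the sentence would let favourable interviews stand as support for measuring BP in pregnant women, in a study that does not check the readings. The sentence that follows links this use to finding women with pre-eclampsia or eclampsia and fever, so a wrong reading would matter. The protocol's own literature review (section 5.0) reports a wearable patch that was accurate for heart rate but not acceptably so for respiratory rate. Accuracy therefore has to be shown parameter by parameter.

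**Working it through.** No formula applies, and the plan gives no figure to reproduce on this point. The only related number, 125 women for Aim 2, comes with no precision target, margin or standard deviation. The check is a comparison of sections and a few counts.

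1. **The inference.** Section 3.0: feasible and acceptable, therefore sufficient evidence for use to measure vital signs and BP.

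2. **What the protocol says about BP.**
   - Section 1.1: early stage, with this study's data feeding the integration of BP into the device.
   - Section 6.0, question 2: whether the photoplethysmograph (PPG) signal can yield an accurate algorithm is something the study asks.
   - Section 7.0, Aim 2: the PPG data train a model.
   - Section 8.0, Data Collection and Data Analysis: the algorithm is developed from these data and piloted afterwards.
   - Section 8.0, Study Design: final validation and field testing come before CE marking is sought.

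   A study that supplies input to an algorithm still to be piloted and validated cannot also be sufficient evidence for using that algorithm.

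3. **What is analysed.** Sections 7.0 and 8.0 describe two things: a thematic analysis of 12 + 12 = 24 interviews (more if saturation is not reached), and development of the BP algorithm. They name no reference reading, held-out test set, error or agreement measure, or acceptance threshold. The reference list includes two items on agreement between measurement methods (16 and 17). The available text does not cite them, so they do not amount to a plan.

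4. **Counts by parameter.**
   - Parameters listed for NeoSpot (section 8.0): 5.
   - Parameters measured by the precursor (section 1.1): 4. Without a precursor basis: 5 − 4 = 1, namely BP.
   - Parameters with a reference measurement or accuracy analysis described in this study: 0 of 5.

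5. **Basis for the other four.** In Table 1, four completed studies list an accuracy purpose: 27 + 15 + 15 + 30 = 87 participants. All four used neoGuard, and none lists pregnant women as its population. This gives indirect support for four parameters and none for BP.

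6. **Development status of BP across sections.** Section 1.1 says early. Section 8.0, Study Design, describes the device as a whole as nearly finished, with on-board algorithms that compute BP. Data Analysis for Aim 2 speaks of developing the algorithm further, which implies that some version exists. These descriptions do not agree.

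7. **Use of BP readings during the study.** Section 8.0, Study Procedures, has NeoSpot BP results passed to the treating team, for up to 125 women. Section 9.0 links abnormal BP to referral. Neither is reconciled with the status given in section 1.1.

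**The case against.** The strongest reply is that this is Rationale prose. No aim, eligibility rule, sample size or analysis depends on it. Section 4.0 and Aim 1 already confine the study to feasibility, acceptability and related outcomes. That stands: the defect changes no data, and a further limiting statement under Data Analysis would largely repeat what is there.

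A second reply is that the protocol says elsewhere what its results are for. Section 3.0 itself gives a modest purpose, to inform changes and considerations for use. Section 1.1 speaks of integrating BP, and section 8.0 of later piloting and of validation before CE marking. That also stands. A reader might infer that the quoted sentence is the protocol's only statement of what a positive result would establish, or that no later accuracy check is foreseen. The documents support neither reading. But if validation is still to come, the evidence from this study is not yet sufficient, so the reply does not rescue the sentence.

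Third, a reader might infer from section 1.1 that no BP algorithm exists yet. The documents do not support that either. The Introduction says the device measures BP, section 8.0 says its algorithms calculate it, and Data Analysis implies an existing version. What can be said is that the status is described inconsistently.

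Fourth, the other four parameters have a stated basis in the precursor's similar hardware and algorithms. That is fair, and it is why the point is weaker for them.

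Finally, the sharing of BP results is a separate matter from the inference in section 3.0. Study Procedures routes results through treating clinicians working to local standard of care, and section 9.0 refers women for further assessment. These are grounds for reconciling the sections, and they add no weight to the main point.

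**Conclusion.** The point holds for BP. The conclusion in section 3.0 is one the described design cannot deliver, and it conflicts with sections 1.1, 6.0 and 8.0. The contradiction covers 1 of 5 parameters. For the other 4, the sentence rests on an expectation carried over from neoGuard that this study does not test. The available text describes an accuracy check for none of the 5.

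The defect lies in what this study is said to show. Aim 1 is not invalidated, and the protocol does foresee later validation.

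This rests on the available text. Two figures at the start of section 8.0 could not be seen. If either shows a reference measurement, the count of 0 would need revisiting.

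**What to change.** Replace the quoted sentence in section 3.0 with:

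> If NeoSpot is found feasible and acceptable, this would support its continued development and subsequent validation; this study does not by itself establish the accuracy of its blood pressure or vital sign readings.

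This is a wording change with no effect on data or sample size. Its cost is a more modest stated conclusion. Research question 2 can stay as a development question.

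Separately, the sponsor must reconcile the descriptions of BP's development status in section 1.1, section 8.0 (Study Design) and section 8.0 (Data Analysis, Aim 2). The claim of immediate clinical application in section 3.0, the sharing of BP results in section 8.0 and the referral text in section 9.0 must be reconciled with them. This may need wording only or may touch procedures, depending on how the sponsor resolves it. No clinical rule is proposed here.

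The new wording does not supply a reference BP measurement for Aim 2, whose absence from the described methods is a separate point.

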4.0 Theoretical/conceptual framework

This study is a feasibility trial, which is designed to demonstrate the feasibility and acceptability of this novel platform when used by community health workers (CHWs) on pregnant women to check their vital signs during community ANC outreach activities.

5.0 Literature review

Patient vital signs monitoring is key to disease management and timely intervention. Measurement of vital signs in in- and out-patients is necessary to assess the clinical situation of the patient and to detect clinical deterioration at an earlier stage, which allows clinicians to take corrective actions.⁷ WHDs like the ViSi Mobile Wireless Sotera and Health Patch Vital Connect that can be used for continuous collection of physiological data have been cleared by the US Food and Drug Agency (FDA) for home and hospital use. In a 2017 feasibility study, Weenk et al. concluded that both ViSi Mobile and Health Patch were promising for continuously monitoring vital signs in hospitalized patients, if the frequency and duration of artifacts could be minimized. The devices were well received and comfortable for most patients.³

In a subsequent study, ViSi Mobile and Health Patch were tested regarding Modified Early Warning Scores (MEWS) calculation and compared to nurse measurements and detection of high MEWS in periods between nurse observations; findings suggested that the wearable devices were more accurate than nurses' observations.⁹

A few other studies about continuous monitoring with wearable technologies on general ward and ICU patients have been published. Martine et al. validated the accuracy of a wireless patch sensor to measure heart and respiratory rate in postsurgical patients at high risk for complications. The novel patch showed high accuracy for measurement of heart rate but accuracy for respiratory rate was outside acceptable limits.¹⁰ In a feasibility study on wearable biosensor devices carried out in Rwanda, researchers observed that wearable devices could be feasibly implemented and that the units provided accurate vital sign measurements in critically ill paediatric and adult patients with sepsis.¹¹

Results from a 2018 study carried out by Downey et al. showed that patients on the surgical ward found the monitoring device to be acceptable in terms of comfort and perceived an enhanced sense of safety.¹² Pavic et al. noted that remote monitoring of health care status in palliative cancer patients with a limited life expectancy was feasible and patients were able to handle the smartphone and sensor- equipped bracelet.¹³ An early evaluation of the agreement between the SensiumVitals digital patch and a widely used clinical monitor was conducted between Oct 2009 - Jul 2010. Overall agreement for respiration and heart rate measurements between digital patch and clinical monitor was satisfactory.¹⁴

Multiple studies have been conducted on the Bio-Beat medical smart-monitoring technology, demonstrating that in all of the tested statistical parameters, the Bio-Beat application is almost equal to the gold standard device, with a correlation of 98.9%.¹⁵

In summary, the published literature on WHDs suggests that these innovative technologies and digital health systems may offer a viable solution towards an affordable, sustainable and scalable model of patient monitoring in resource-limited settings.

6.0 Research questions

1. Is the NeoSpot a feasible, acceptable, and easy to use device when used by CHWs during community ANC outreach activities?
2. Can photoplethysmograph (PPG) sensor data from NeoSpot be used to develop an accurate and reliable blood pressure algorithm?

7.0 Specific Aims

Aim 1: To describe the feasibility, acceptability, ease of use, and perceived confidence of pregnant women and CHWs to use the NeoSpot device during community ANC outreach

The novel test device, NeoSpot will be used by 12 CHWs during community ANC outreach activities to measure vital signs among pregnant women in Lusaka, Zambia. Through in-depth interviews (IDIs), we will determine and feasibility, acceptability, and ease of use, including design feedback, of the device by 12 CHWs and 12 pregnant women.

Aim 2: To obtain raw PPG data from the prototype NeoSpot device which will be used in the development of an accurate and reliable blood pressure algorithm.

During community ANC outreach activities, CHWs will take readings with the NeoSpot device from 125 pregnant women. The raw PPG sensor data will be used to train an autonomous machine learning model to extract arterial blood pressure systolic and diastolic values.

